23.1 Level of blinding

By the nature of the interventions used within this study, blinding of the participants, clinicians and the researchers is not possible. However, those involved in the analysis of the data will be blind to treatment allocation.

24. Measures to avoid/ minimising bias

Potential sources of bias will be minimised by having minimal exclusion criteria, randomisation, standard training of clinicians guided by a treatment manual, measures of treatment fidelity and adherence to the manual, validated outcome measures and an intention to treat analysis.

25. Data collection

All information collected during the course of the trial will be kept strictly confidential. Information will be held securely in paper format at York Trials Unit, University of Huddersfield University College London and within the R&D departments of each participating Trust and electronically at York Trials Unit. All trial data will be identified using a unique trial identification number. Analytical datasets will not contain any identifiable information. Data will be archived for a period of 5 years following the end of the study.

25.1 Baseline data

At baseline, information will be collected from the participant regarding sexual risk behaviour perceptions, knowledge, sexual stigma, condom use and attitudes, selfefficacy, drug and alcohol use, quality of life, sexual health service use and demographics.

25.2 Follow up data collection

Participants will be followed for a total of 24 weeks. Follow up data collection will be conducted at 3 months (12 weeks) and 6 months (24 weeks) post-randomisation for both groups. We will operate strict "windows" for data collection. At three-month follow-up data collection window will operate from the start of week 11 to the end of week 14. If data is not collected within that time period, this is not pursued and the next time point will be focused on. The 6 month follow-up data collection window will operate from the start of week 23 to end of week 26.
Members of the RESPECT research team will arrange face to face appointments with participants; during these appointments the researchers will collect follow up data covering the main and secondary outcome measures.

The researchers will record missed appointments, as well as how many times they contacted (by text, phone or via case managers) to arrange follow-ups.

26. Qualitative data

There will also be qualitative interviews to gather data on acceptability and feasibility from the perspective of the participants using a sub-sample of consenting participants (see section 13)

27. Data related to fidelity to the intervention

At the end of each session, a short form will be completed by the clinicians delivering the intervention. This will list the content of the session with the clinician ticking what was covered during the session and space to make any additional notes or observations. In addition the participant will be invited to complete a very brief evaluation form.

28. Table of data collection schedule

Event	Time period	Data collected
Pre	Day 0	Consent for study; Baseline CRF:
		Feedback form for refusers

		Randomisation: including confirmation of consent; contact details; confirmation of baseline questionnaire completion
1	1-2 weeks	Intervention participants – First appointment: time of session; the length of session; participant attendance; therapist involved; location; and any materials used.
		Audio recording of sessions
2-6	2-12 weeks	Intervention participants subsequent appointments: time of session; the length of event; participant attendance; therapist involved; location; any materials used.
		Audio recording of sessions.
3	12 weeks	Three month CRF: follow-up.
4	24 weeks	Six month CRF: follow-up. Exit questionnaire
		We will undertake semi-structured qualitative interviews with participants from intervention and TAU groups to gather data on acceptability and feasibility of both the study and the intervention.

We will conduct post-study de-brief sessions with the interventionists to gather information and feedback about delivery of the intervention in order to inform any future model of roll-out in a subsequent study.

29. Completeness of data

As data collection is being undertaken by face to face appointments with researchers at baseline and follow up assessments, it is anticipated that missing data will be minimal with the exception of those participants who do not attend/engage with appointments or follow up and researchers are not able to locate.

30. Data handling and storage

Information with regards to the study participants will be kept confidential and managed in accordance with the Data Protection Act, NHS Caldicott Guardian, Research Governance Framework for Health and Social Care and the Health Research Authority.

Personal addresses, postcodes and other contact details of consenting participants will be stored on a secure password protected server located at the University of York, for the purposes of assisting in follow-ups during the study. All paper data collected from participants will be maintained in a safe secure environment at each of the research team sites. Paper records will be identified using identifiers rather than personally identifiable information.

Participants allocated to the sexual health intervention will be asked to give permission to have their intervention session(s) audio recorded. These data will be used by the research team to assess clinician fidelity to the intervention manual at the end of the treatment. All recordings will be identified by an identification number rather than personal information. Research findings addressing the process of the intervention may contain anonymised participant quotations. These recordings will be archived in a secure location for a minimum period of 10 years.

Data will be collected through questionnaires designed on paper. Scanned data from the paper forms are stored in a download database where they are checked against the hard copy of the questionnaire. Data is error checked and then validation checks are run against the validate database. Discrepancies identified during validation which require resolution are communicated to the relevant person who is in a position to be able to obtain the information required to rectify the discrepancy. Analytical datasets will not contain any identifiable information. Data will be archived for a minimum period of 10 years following the end of the study.

Qualitative interview participants' confidentiality will be ensured by assigning a unique identification code to electronic sound files and transcripts of individual interviews, known only to the qualitative researcher and appropriate members of the research team. Any personal information required will also be coded with this identification number and kept in a password protected electronic file or separate filing cabinet which will be locked at all times. Any quotes published will be anonymous further protecting participant confidentiality. All qualitative data will be stored and analysed at the University of Huddersfield.

31. Treatment fidelity

A simple tick list will be completed for every session indicating what content of the manual was covered in each session and space for any comments about how it was implemented, and any modifications made. This will be completed by the interventionist. Participants receiving the intervention will also be asked to complete a short evaluation sheet at the end of each session and these will cover usefulness, relevance and levels of comfort for each session. Where consent is given, intervention sessions will be audio recorded and used for fidelity checks. The research team will listen to a 10% random sample (no more than 15 sessions) to assess clinician fidelity and adherence to the intervention protocol. Should a participant not be willing to have their sessions audio recorded (which can be indicated on the consent form), this will not affect their treatment nor preclude them from participating. These audio recordings will be stored and archived securely at the University of Huddersfield for the northern sites, and at UCL for the southern sites.

32. Clinician interviews

The clinicians delivering the sexual health intervention at each site will be invited to participate in a focus group/debriefing session at the end of the intervention delivery. The purpose of this single session is to explore a number of themes, including the training and implementation process, their views around sustainability and capacity, and around use of the intervention in routine clinical practice in mental health services. This single session will seek to identify any problems that clinical staff encountered in delivery of the intervention and the trial process, with a view resolving these in a full trial.

33. Statistical considerations

33.1 Sample size

This will be an external feasibility trial, the main purpose of which is to assess feasibility of the new intervention and the methods of recruitment, randomisation and follow up for a full trial in a population with SMI. The sample size calculations are based on estimating attrition and standard deviation of the primary outcome. Assuming 30% of participants are lost to follow up (as in the SCIMITAR trial (Gilbody et al, 2015) with a sample size of 100, then the 95% confidence interval for this level of attrition will be the observed difference ±9 percentage points (i.e. between 21% and 39%; Hertzog, 2008). Hence an external pilot trial of 100 participants should ensure robust estimates of follow-up in this population. Furthermore, an external feasibility study of at least 70 measured subjects will provide robust estimates of the standard deviation of the outcome measure to inform the sample size calculation for the subsequent larger definitive fully powered trial (Teare, 2014).

34. Planned recruitment rate

It is expected that recruitment will be on average 16 patients per month. Should recruitment fall below the expected rate, we will meet with the sites to review progress and discuss any problems and take any necessary action in order to resolve any issues affecting recruitment. As well as the named teams/locations within each organisation for targeting the recruitment we have also identified other potential service locations within each organisation where we could increase the potential for recruitment.

35. Qualitative research

As well as obtaining data relating to the stated outcome measures, follow-up interviews will be conducted at six months post-randomisation. These will be undertaken by the RESPECT researchers as well as lived experience researchers who are part of the RESPECT steering group. The key aims of the qualitative interviews are to establish the acceptability and feasibility of the intervention itself, as well as the methodology and processes used throughout the trial. The qualitative process evaluation will run concurrently throughout the study. The qualitative study will aim to recruit a purposive sample of participants from both arms of the study. Approximately 20 participants will be recruited at the end of the intervention period; ten from the intervention and ten from the control group (which represents approximately 20% of people who will be recruited). We will attempt to recruit approximately equal numbers of males and females. We will also recruit approximately equal numbers from each site. In addition we will also be mindful of the demographic variance in the catchment areas for example; it is likely that Camden and Islington will be more ethnically diverse than Yorkshire.

The RESPECT researchers will be trained in qualitative interview techniques and will use interview topic guides in order to standardise procedures across all interviews. The interviewer will seek to establish satisfaction with the treatment received and perceived processes of change, including helpful aspects of the therapeutic process. This will complement the analysis of the quantitative data and identify ways in which the intervention may need to be modified in preparation for a definitive trial.

Additionally, the clinicians delivering the sexual health intervention at each site will be invited to participate in a focus group/debriefing session at the end of intervention
RESPECT Protocol_v1.3 15.12.16 Page 4

delivery. This will focus on delivery of the intervention, content of the intervention, barriers and solutions to delivery as well as sustainability and implementation across clinical practice.

All people who gave consent to be contacted will be sent a brief feedback questionnaire to complete and return to give feedback on how they found they recruitment process. In addition, all people entered into the study (who haven't officially withdrawn) will be sent an exit questionnaire to complete about their experiences of the study.

36. Interview format

The interviews will be by telephone. They will be semi-structured in nature and based around a topic guide. The topic guide will cover areas including characteristics of the setting, mode of delivery, satisfaction and acceptability of the intervention, aspects of the intervention that were helpful or unhelpful from the participant's perspective, intensity and duration of the intervention, the overall experience of the treatment and suggestions for improvement to the intervention. The topic guide will also cover processes related to trial methodology including views on the consenting process, randomisation, outcome measures used and other methodological factors.

37. Transcription and analysis of data

For the purpose of data analysis, all interviews will be recorded and transcribed; content analysis will be conducted independently by a minimum of two researchers and discrepancies in coding will be resolved through discussion until consensus is reached. Analysis will be conducted using the framework approach. This deductive approach to qualitative analysis allows for a more structured approach to data collection based on pre-determined aims and objectives. Software (NVivo version 10) will be used to synthesize and code the data within a thematic matrix to enable elucidation of conceptual associations. Both pre-determined concepts used for developing the interview schedules as well as emergent themes arising from the data will inform the process of identifying the key thematic categories to be used in data coding, which will then be used to index and chart findings.

38. Data management

All data from the trial will be collected using paper-based forms (baseline booklet, intervention session forms; follow-up booklets). Researchers and clinicians will be responsible for ensuring the completeness and reliability of the data from their site, and then for transferring records to York Trials Unit. Data from paper forms will then be entered into a master database for the trial using either optical scanning techniques or entered manually.

39. Statistical Analysis

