RESPECT

Randomised Evaluation of Sexual health Promotion Effectiveness informing Care and Treatment (RESPECT): a feasibility study of an intervention aimed at improving the Sexual Health of People with Severe Mental Illness

PROTOCOL Version 1.3_15.12.16

Authorised b	y:			
Name:	[name]	[name]	 Role:	Chief Investigator
Signature:			Date:	15.12.16

Institutions:

University of Huddersfield University of York, Department of Health Sciences University College, London Brighton and Sussex Medical School

Sponsor:

[name] [name] Dean, Human and Health Sciences University of Huddersfield [name]

NHS National Institute for Health Research

TITLE	Randomised Evaluation of Sexual health Promotion	
	Effectiveness informing Care and Treatment (RESPECT): a	
	feasibility study of an intervention aimed at improving the	
	Sexual Health of People with Severe Mental Illness	
Short Title	The RESPECT Study	
Protocol Version 1.3		
Protocol Version		
Date	15.12.16	
ISRCTN	ISRCTN15747739	
Methodology	Pragmatic, randomised controlled, open feasibility trial delivered	
	in community mental health services within four NHS Trusts.	
Fundar.		
Funder	NIHR HTA Programme grant number 14/172/01	
Sponsor	University of Huddersfield	
Study Duration	14 months	
Study Centres	Community mental health services in:	
	Leeds and York Partnership NHS Foundation Trust; Camden	
	and Islington NHS Foundation Trust; Sussex Partnership	
	NHS Foundation Trust and South West Yorkshire Partnership	
	NHS Foundation Trust	
Objectives	To demonstrate the feasibility of recruiting people with SMI to a	
	sexual health intervention and the feasibility of delivering the	
intervention in a community mental health services. To		
the level of treatment retention and explore through qual		
	interviews the participants' views, acceptability and experiences	
	of the intervention and the study process.	

Number of Subjects/Patients	One hundred participants will be recruited to the trial on the basis of 30% sample attrition, expecting data to be successfully collected on 70.
Main Inclusion Criteria	People currently in treatment (Care Programme approach) in the community mental health services diagnosed with a severe mental illness and aged over 18.

Study Summary

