39.1 Quantitative analyses

The flow of participants through the trial will be detailed in a CONSORT flow diagram. The number of people screened, randomly assigned, receiving the intervention, completing the study protocol and providing outcome data will be summarised overall and by trial arm. The number of individuals withdrawing from the intervention and/or the trial and any reasons for withdrawal will be summarised by trial arm. To quantify the acceptability of the intervention the number of sessions attended will also be summarised. All data will be presented descriptively with no formal statistical analyses undertaken. For each data collection point and outcome measure, the number of nonresponders will be calculated and completion rates compared. The potential impact of therapist effects may be explored using ICC and the average caseload per therapist will be detailed.

40. Analysis of economic and quality of life data

The economic component of the study will be designed to assess the feasibility of conducting a cost-effectiveness analysis of a full trial. This will involve piloting a short questionnaire, analysing responses and calculating Quality Adjusted Life Years (QALY) changes using the EQ-5D. We would not expect to see significant changes between groups due to the small sample size in this feasibility trial.

A simple questionnaire will measure participants' use of health care and will be identified retrospectively by means of service use questions. The economic analysis will assess the feasibility of using such a questionnaire in this population. The questionnaire will ask about primary care, sexual health and family planning services. In the full trial resource use data will be multiplied by national average unit costs to calculate per participant costs in the 3 month period before the intervention and the 3 month period after receiving the sexual health intervention or TAU.

Quality of life will be measured by EQ-5D at baseline and each follow up time point. The use of EQ-5D enables the estimation of QALYs. Measuring health status using QALYs follows the recommendations of NICE¹ and enables the value for money afforded by treatments to be compared to a range of other health care interventions.

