This study is being co-ordinated and conducted by the University of Huddersfield, York Trials Unit (University of York) and University College, London. The research has been funded by the National Institute of Health Research Health Technology Research Programme.

NHS Indemnity will apply for patients treated within NHS sites. The University of Huddersfield, University College, London and the University of York will provide legal liability cover for their employed staff. Non-negligent harm will not be covered.

50. Reporting and dissemination

The results from this study will be submitted to the funders, peer-reviewed journals and presented at relevant meetings/conferences.

51. Project timetable

RESPECT Timeline				
Task	Date			
Submit to NHS Ethics Committee	July 2016			
Training intervention staff	Sept 2016			

RESPECT Timeline				
Task	Date			
In NHS Sites: promotion of study, training of CSOs, printing of study materials	Sept 2016			
NHS Ethics and Site governance in place	Sept 2016			
Recruitment and baseline data collection	Oct 2016 – March 2017			
Follow up date collection	Dec 2016 – September 2017			
Fidelity Monitoring	Oct 2016 – March 2017			
Qualitative data collection: interviews with participants	March 2017			
Staff focus group	May 2017			
Data input and cleaning	Sept 2016 – Sept 2017			
Quantitative Analysis	April 2017 – Nov 2017			
Qualitative analysis	April 2017 – Nov 2017			
End of Project Review meeting	Dec 2017			
Write-up and outputs	Oct 2017 – Jan 2018			

52. Appendix 1:Study flow diagram

53. References

Angelino, A. F. & Treisman, G. J. 2008. Issues in co-morbid severe mental illnesses in HIV infected individuals. *International Review of Psychiatry*, 20, 95-101.

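### Minor: at the planned 16 per month the six-month recruitment window yields 96, not 100, and section 33.1 words an expected yield of 70 as a minimum and a single proportion as a difference

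*Protocol*

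**What the plan says.** - **Yield.** The Protocol's summary table states: "One hundred participants will be recruited to the trial on the basis of 30% sample attrition, expecting data to be successfully collected on 70".
- **SD argument.** Section 33.1 says that "an external feasibility study of at least 70 measured subjects will provide robust estimates of the standard deviation of the outcome measure".
- **Attrition precision.** Section 33.1 begins "Assuming 30% of participants are lost to follow up" and, for a sample of 100, says that "the 95% confidence interval for this level of attrition will be the observed difference" ±9 percentage points, spelled out as 21% to 39%.
- **Rate and trigger.** Section 34 states: "It is expected that recruitment will be on average 16 patients per month". If recruitment falls below the expected rate, the team meets the sites and acts. Further service locations have been identified as a reserve.
- **Window.** In the section 51 timetable, the row "Recruitment and baseline data collection" runs from October 2016 to March 2017, and follow-up data collection ends in September 2017. Section 25.2 closes the six-month follow-up window at the end of week 26.
- **Target.** Section 14 repeats the target of 100 and estimates that up to 300 people could be recruited.

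**The concern.** The planned rate, the window and the target do not agree. Because section 34 uses the same rate as its trigger, recruitment could run exactly to plan and finish short without prompting the review meant to catch a shortfall.

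Section 33.1 also uses 70 as a lower bound, while the summary table uses it as the expected value. The sample size has no reserve above that expectation, so the two statements describe different quantities.

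Finally, section 33.1 calls its attrition interval a difference, although the calculation concerns one proportion in the whole sample. At stake is whether the planning figures can be taken at face value when recruitment is monitored and when this study is used to plan the main trial.

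**Working it through.** **1. The plan's own figures reproduce.**
- Inflation for attrition: 70 / (1 − 0.30) = 100, and 100 × 0.70 = 70.
- Attrition interval: 1.96 × √(0.30 × 0.70 / 100) = 0.0898, or ±9.0 points, giving 21% to 39%. This is the standard formula for one proportion with n = 100.

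**2. Rate against window.** Inputs: 16 per month (section 34), read as the total over the four sites; six calendar months, counting October and March in full (section 51), the longest reading of that row; target 100.
- Recruits at the planned rate: 16 × 6 = 96.
- Rate needed: 100 / 6 = 16.7 per month. At 17 per month: 17 × 6 = 102.
- Time needed at 16 per month: 100 / 16 = 6.25 months.
- Expected number measured from 96: 96 × 0.70 = 67.2.

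**3. Room to run on.** A participant randomised on 31 March 2017 reaches the end of week 26 (182 days) on 29 September 2017. Follow-up ends in September 2017. Anyone randomised later either has a shortened six-month window or overruns the timetable.

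**4. What 70 means.** Over the Protocol's attrition interval, the number measured from 100 runs from 100 × (1 − 0.39) = 61 to 100 × (1 − 0.21) = 79. Exact binomial probabilities of measuring at least 70:

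| True attrition | 100 recruits | 96 recruits |
|---|---|---|
| 21% | 0.99 | 0.94 |
| 25% | 0.90 | 0.73 |
| 30% | 0.55 | 0.31 |
| 35% | 0.17 | 0.06 |
| 39% | 0.04 | 0.01 |

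**5. Does it matter for the SD?** Relative standard error of an SD, approximately 1 / √(2(n − 1)), for a normally distributed outcome:
- n = 70: 1 / √138 = 8.5%
- n = 67: 1 / √132 = 8.7%
- n = 61: 1 / √120 = 9.1%
- n = 79: 1 / √156 = 8.0%

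The 95% limits for the true SD are 0.857 to 1.200 times the estimate with 70 measured, and 0.855 to 1.205 times with 67.

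**6. Does it matter for attrition?** With 96 recruits the half-width is 1.96 × √(0.21 / 96) = 0.0917, or ±9.2 points instead of ±9.0.

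**The case against.** The strongest reply is that nothing in the design fails. Dividing by one minus the attrition rate is the standard method. It makes the expected yield equal the requirement, so a probability near one half of reaching that number follows from the method and is not a mistake in N. Section 33.1 can be read as saying what size suffices, with the summary table giving the expected yield. This stands. A reader might infer that the design does not deliver its 70, but the documents do not support that. Nor do they show that anything changes at exactly 70: precision is nearly the same at 67.

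On recruitment, 16 is an average and close to 16.7. The Trial Management Group reviews recruitment every two months whatever the rate (section 47.2), and the pool and reserve locations are ample. So a shortfall would probably be noticed. But the stated rate still does not give the stated target in the stated window, and section 34's own trigger would not respond.

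On the word difference, the same sentence names a level of attrition and gives 21% to 39%, so few readers would be misled. It remains the wrong term.

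Two further inferences are tempting:
- **That section 39.1 excludes the interval used to justify the sample size.** It says: "All data will be presented descriptively with no formal statistical analyses undertaken". Descriptive presentation does not exclude confidence intervals, and which ones to report may be left to the SAP, which is not shown.
- **That the main trial will be under-sized.** This presumes that the bare SD estimate will be carried forward. Section 33.1 says only that it will inform that calculation.

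**Conclusion.** The point holds as a minor one: three figures or terms are wrong as written. Section 34's rate, which is also its review trigger, falls four participants short of the target over the six-month window (96 against 100), with about 67 expected to be measured. The 70 in section 33.1 is the expected number at 30% attrition, with 61 to 79 over the Protocol's own interval. The ±9 points describes one pooled proportion.

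This rests on reading 16 as the total rate over the four sites, on counting six full calendar months, and on the Protocol's 30% attrition. The 55% chance of 70 or more is sensitive to that last figure.

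The consequences are small. SD precision and the attrition interval hardly move, and N = 100 stands. Whether 70 is a threshold in the cited simulation study cannot be checked from the Protocol.

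**What to change.** - **Section 34:** set the expected rate, and so the review trigger, at 17 per month (100 / 6 = 16.7).
- **Section 33.1, SD sentence:** replace the minimum with an expectation, for example: we expect 70 measured participants at 30% attrition, with about 61 to 79 if attrition lies between 21% and 39%.
- **Section 33.1, attrition sentence:** replace difference with proportion, and say that the ±9 points applies to the pooled sample of 100.

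The cost is wording only, with no extra participants. The stated yield looks slightly less favourable, and the review may be triggered slightly earlier.
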